#### 9.6.6 Archival Tumor Tissue: Exploratory

Archived tumor tissue from the most tumor recent resection demonstrating active tumor will be collected from all patients, when sufficient tissue is available. If sufficient tissue is not available from the most recent surgery, then tissue from an earlier surgery is acceptable, if available, including from the initial resection at diagnosis.

At the time of registration, prior to beginning treatment, a tumor tissue form indicating availability must be completed and signed by a pathologist for each study participant. This form provides written documentation of the availability of tissue for this study and the pathologist's agreement to send it as described below.

20 unstained slides, preferentially from the most recent tumor resection, will be requested. The associated pathology report from the institution of collection should be shipped with the slides.

Details for the collection and shipment of tissue samples are provided in the **Laboratory Manual**.

## **10.0 OFF TREATMENT/OFF STUDY CRITERIA**

Each subject has the right to withdraw from the study at any time without prejudice. The investigator may discontinue any subject's participation for any reason, including adverse event or failure to comply with the protocol (as judged by the investigator such as compliance below 80%, failure to maintain appointments, etc.).

Should a subject withdraw from the study, the reason must be stated on the case report form, and a final evaluation of the subject should be performed.

Patients who go off treatment must be followed for adverse events (AEs) for at least 30 days from the last dose of encorafenib and binimetinib.

### **10.1 Off Treatment Criteria**

In the absence of treatment delays due to adverse event(s), treatment may continue until one of the following criteria applies:

- Disease progression on MRI as determined by the local site
- Intercurrent illness that prevents further administration of treatment
- Unacceptable adverse event(s)
- Patient decides to withdraw from the study
- General or specific changes in the patient's condition render the patient unacceptable for further treatment in the judgment of the investigator
- Clinical progression
- Patient non-compliance
- Pregnancy
  - All women of child bearing potential should be instructed to contact the investigator immediately if they suspect they might be pregnant (e.g., missed or late menstrual period) at any time during study participation.
  - The investigator must immediately notify CTEP in the event of a confirmed pregnancy in a patient participating in the study.
- The drug manufacturer can no longer provide the study agent

The reason(s) for protocol therapy discontinuation, the reason(s) for study removal, and the corresponding dates must be documented in the Case Report Form (CRF).

## **10.2 Off Study Criteria**

Patients will only be off study at the time of death. All patients will be followed for survival every 2 months for the first two years from the off-treatment date; after 2 years, patients will be followed every 6 months until death. Survival status may be obtained by phone call, clinic visit, or medical records (e.g. physician notes/laboratory results of clinic or hospital visit). Please note that additional survival status reports will be required twice yearly for ABTC Central Office reporting.

## **11.0 STATISTICAL CONSIDERATIONS**

### **11.1 Study Design/ Endpoints:**

This is a non-randomized, open-label, multicenter study of evaluating treatment efficacy and safety of encorafenib in combination with binimetinib in adult patients with recurrent BRAF-V600 mutated high-grade primary brain tumors. The study includes a total of four study cohorts. The Cohort 1 includes patients with high-grade glioma (including but not limited to glioblastoma (GBM), anaplastic astrocytoma (AA), and gliosarcoma). The Cohort 2 includes patients with anaplastic PXA that is recurrent after first-line treatment. The cohort 3 includes patients with recurrent high-grade brain tumor that is not included in the cohort 1 and 2, and the cohort 4 is a surgical cohort. All subjects must have histologically confirmed high-grade primary brain tumors.

The three treatment cohorts are independent subtypes of the high-grade primary brain tumors. No randomization is required for patient allocation on to each cohort.

The primary objective of the study is to evaluate efficacy of encorafenib in combination with binimetinib to treat patients with recurrent BRAF V600E/K-mutated malignant glioma (MG) and anaplastic pleomorphic xanthastrocytoma (PXAs).

The primary endpoint is tumor radiographic response per RANO criteria (Section [8.1](#)) for the three treatment cohorts.

### **11.2 Sample Size Justification**

Sample size consideration for cohort 1 malignant gliomas (MG) and cohort 2 anaplastic PXAs:

Based on the information from prior clinical trials (Scientific rationale), the investigators consider the primary cohorts 1 (patients with AA or GBM) and 2 (Anaplastic PXAs) to share a similar null hypothesis of tumor response rate at 10% to be considered not clinically meaningful treatment effect and an alternative of 30% tumor response rate to be clinically desired treatment effect. A total of 23 patients is required per individual primary cohort 1 and cohort 2.

Cohort sample size estimation was based on a 2-stage design (minimax) with a futility analysis at end of first stage. Fourteen patients will be enrolled onto first stage. If no more than 1 response (7%) was observed among the initial 14 patients in a cohort, the cohort

would be terminated early and declared negative. Otherwise, nine more patients will be enrolled. If at least 5 responses (at least 22%) were observed among the 23 evaluable patients, the regimen would be considered worthy of further testing in this disease and the patient population. This design yields at least 85% power to detect a true response rate of at least 30% at a false positive rate of 10%. It yields at least 0.9 probability of a negative result if the true response rate is no more than 10%, with at least 0.58 probability of early negative stopping. The 2 primary cohorts will be evaluated independently.

The maximum total sample size for the two primary cohorts is 46 patients (23+23).

The sample size for the cohort 3 is 6 to 10 patients (other types of high-grade brain tumor that are not included in the primary cohort 1 or 2). This sample size is not based on statistical rationale but due to clinical feasibility. Patient enrollment will be considered completed at the time of completion of the enrollment in the cohort 1 and the cohort 2.

In the correlative studies, there is a surgical cohort of 6 patients who are clinically surgical indicated for tissue PK study after initial treatment prior to surgery. There is no clinical or trial decision will be made based on outcome of the surgical cohort. Currently, prior information on amount of drug concentration in tumor tissue are lacking, especially with this combination treatment. However, 6 patients will have 90% power to detect an 80% true probability of BBB penetration, with .93 likelihood of rejecting a 30% true probability of BBB penetration.

Data analysis will be performed for each cohort independently. Tumor response rate will be estimated as proportion of number of tumor responders over number of patients in a cohort, as a binomial distribution (exact method) with 80% and 90% confidence intervals.

**Accrual Rate:** The expected accrual rate is one patient per month among 11 ABTC institutions.

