## Surgical Arm Treatment Schema

Subjects in the surgical cohort must be candidates for a clinically-indicated surgery and must have a BRAF V600E/K-mutated high-grade glioma or a low-grade glioma with high clinical suspicion for progression to high-grade. These subjects will take encorafenib and binimetinib in combination at their FDA-approved doses (see Section 4.3 for administration details) for 10-14 days prior to surgery, with a preference for 14 days, though a minimum of 10 days is acceptable. The last dose of both drugs will be administered two hours prior to surgery. Specimens will be collected as described in Section 9.6 and processed as described in the **Laboratory Manual**.

After surgery, the subjects will not take further encorafenib or binimetinib until a study visit to assess their neurological exam, physical exam (or telemedicine physical evaluation), and performance status, at 2-6 weeks post-operatively. At time of restarting combination treatment, subjects will follow the schedule listed above for the medical cohort, and will continue treatment as defined in Section 10.1.

Patients with histopathology inconsistent with high-grade glioma (either treatment effect or low grade glioma) will be replaced. Overall survival will be assessed from the first day that patient receives drug to death from any cause.

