### **Progressive Disease – PD (defined by *any* of the following):**

- a) **For HGG RANO:**  $\geq 25\%$  increase in sum of the products of perpendicular diameters of enhancing lesions compared to the smallest tumor measurement obtained either at baseline (if no decrease) or best response, on stable or increasing doses of corticosteroids.\*
- b) Any new enhancing or non-enhancing lesion.
- c) Clear clinical deterioration not attributable to other causes apart from the tumor (e.g., seizures, medication adverse effects, complications of therapy, cerebrovascular events, infection, etc.) or changes in corticosteroid dose. The definition of clinical deterioration is left to the discretion of the treating physician, but it is recommended that a decrease in 20% of KPS or from any baseline to 50% or less be considered, unless attributable to comorbid events.
- d) Failure to return for evaluation due to death or deteriorating condition.
- e) Clear progression of non-measurable disease.

\* Stable doses of corticosteroids include patients not on corticosteroids.

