### 9.3 Adverse Events: Lists and Reporting Requirements

Patients will be evaluated for toxicity if they have received at least one dose of encorafenib and binimetinib.

Adverse event (AE) monitoring and reporting is a routine part of every clinical trial. The following list of AEs (Section 9.3.1) and the characteristics of an observed AE (Section 9.3.2) will determine whether the event requires expedited reporting via the CTEP Adverse Event Reporting System (CTEP-AERS) **in addition** to routine reporting.

Adverse Events will be collected for at least 30 days following the last dose of study drug.

All adverse events must be reported to the ABTC Central Office and the NCI in the manner described and per the requirements of the investigative site’s Institutional Review Board.

Adverse events will be entered into CTEP’s iMedidata Rave database by the investigative site in a timely manner. See Section 12.0 – Records to be Kept.

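### Does the undefined word evaluable in the final go rule leave the primary response decision without a usable denominator?

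*Combined protocol and SAP*

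**What the plan says.** Section 11.2 sets a two-stage minimax design for each primary cohort. The two cohorts "share a similar null hypothesis of tumor response rate at 10" percent, with 30% as the rate of interest. Three phrases describe who is counted:

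- Futility look: "If no more than 1 response (7%) was observed among the initial 14 patients in a cohort", the cohort stops.
- Final rule: "If at least 5 responses (at least 22%) were observed among the 23 evaluable patients", the regimen is considered worth further testing.
- Estimation: "Tumor response rate will be estimated as proportion of number of tumor responders over number of patients in a cohort", with exact 80% and 90% intervals.

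Enrolment is 14 and then nine more. On the total, the section says "The maximum total sample size for the two primary cohorts is 46 patients (23+23").

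Elsewhere, Section 9.3 gives an inclusion rule for safety: "Patients will be evaluated for toxicity if they have received at least one dose of encorafenib and binimetinib". There is no matching sentence for response. The only replacement rule is in the surgical arm schema (Section 4.1): "Patients with histopathology inconsistent with high-grade glioma (either treatment effect or low grade glioma) will be replaced". Section 8.1 lists as progressive disease "Failure to return for evaluation due to death or deteriorating condition", and treats an unconfirmed complete or partial response as stable disease. Section 8.2 defines a responder as someone whose response lasts at least 4 weeks, with central neuroradiology review making the final determination.

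**The concern.** Three descriptions of the population for one primary endpoint invite the question of which one governs. The final rule uses a qualifier that the futility look and the estimate lack, and the qualifier is undefined. Enrolment is capped at 23 per cohort, and the study maximum of 62 in Section 3.1 is fully used (46 + 10 for cohort 3 + 6 surgical), so there is no slack for replacements. If one treated patient has no usable post-baseline scan for a reason other than death or deterioration, a set of 23 evaluable patients cannot be assembled.

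The trial is open-label and single-arm, and its go decision turns on one response (5 against 4). A population settled after responses are known could in principle shift the error rate or the power. A cohort could also pass on one denominator and be reported on another.

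**Working it through.** **Inputs (Section 11.2).** Null rate 0.10; alternative 0.30; stage 1 n = 14, stop at 1 or fewer; total n = 23, positive at 5 or more. Stated properties: power at least 85%, false positive rate 10%, probability of early stopping under the null at least 0.58. The documents give no non-evaluable rate, so every loss below is an assumption.

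**Step 1: reproduce the design with all 23 counted.**

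P(early stop) = P(X1 ≤ 1), with X1 ~ Bin(14, p). At p = 0.10: 0.2288 + 0.3559 = 0.585.

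P(positive) = Σ over x = 2 to 14 of P(X1 = x) × P(X2 ≥ 5 − x), with X2 ~ Bin(9, p).

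| Stage 1 responses | Contribution at p = 0.10 | Contribution at p = 0.30 |
|---|---|---|
| 2 | 0.2570 × 0.0530 = 0.0136 | 0.1134 × 0.5372 = 0.0609 |
| 3 | 0.1142 × 0.2252 = 0.0257 | 0.1943 × 0.8040 = 0.1562 |
| 4 | 0.0349 × 0.6126 = 0.0214 | 0.2290 × 0.9596 = 0.2198 |
| 5 or more | 0.0092 | 0.4158 |
| Total | **0.070** | **0.853** |

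The stated properties hold when the 23 are simply the 14 + 9 enrolled.

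**Step 2: can the rule be met with a non-evaluable patient?** Yes. It asks for 5 responses, and 22 or fewer scanned patients can supply them. Calling a non-responder non-evaluable, without replacing that patient, leaves the count and therefore the decision unchanged. Even if the bar is read as the proportion 5/23 = 21.7%, it stays at 5 with up to four patients lost: 4/22 = 18.2%, 4/21 = 19.0%, 4/20 = 20.0% and 4/19 = 21.1% all fall short.

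**Step 3: what status does an unscanned patient have?** Under Section 8.2 a responder needs a response that lasts at least 4 weeks. A patient without a scan cannot meet that, so cannot add to the count at either stage. The estimate is over all patients in the cohort, so that patient is in its denominator. The two treatments agree.

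**Step 4: readings under which the properties move.**

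*30% taken as a rate among evaluable patients, no replacement, at least 5 kept.* The range covers a loss in stage 2 or in stage 1.

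| Patients lost | Power | Error |
|---|---|---|
| 1 | 0.827 to 0.820 | 0.060 to 0.059 |
| 2 | 0.796 to 0.781 | 0.051 to 0.049 |

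*Non-responders excluded and replaced until 23 are evaluable.* With f the share excluded, the rate among those counted becomes p/(1 − f).

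| Excluded | f | Error: rule at 0.10/(1 − f) | Power: rule at 0.30/(1 − f) |
|---|---|---|---|
| 1 of 24 | 0.042 | 0.081 | 0.880 |
| 2 of 25 | 0.080 | 0.093 | 0.904 |
| 3 of 26 | 0.115 | 0.106 | 0.924 |
| 20% | 0.200 | 0.146 | not computed |

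Error reaches 0.10 at f of about 0.10. Every row enrols more than 23.

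**Step 5: rule against estimate.** Under that second reading, with 5 responses and 3 patients replaced, the rule would see 5/23 (21.7%, exact 80% interval 11.0% to 36.6%) and the estimate would be 5/26 (19.2%, 9.7% to 32.8%). The 80% interval then crosses 10%. The planned 90% interval for 5/23 is 9.0% to 40.4%, so it already includes 10% with nobody replaced. The go rule is not tied to either interval.

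**The case for a change.** The best case for a change is that the plan states who is in the safety population and does not do so for the primary endpoint. The first scheduled response scan comes at about 8 weeks, and Sections 10.0 and 10.1 allow earlier exit for withdrawal, non-compliance or adverse events. Such patients are plausible, and Section 11.2 does not say how they enter the final rule. A sentence would cost nothing, and settling the matter before responses are known is good practice in an open-label trial.

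Part of this stands. The word is undefined, and no replacement rule is stated for cohorts 1 and 2. If the sponsor meant 30% as a rate among evaluable patients, counting losses as non-responses lowers power to 0.815 at an assumed 5% non-evaluable (true rate 0.30 × 0.95 = 0.285) and to 0.771 at 10% (0.27).

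The claimed consequences do not follow. Error inflation needs a replacement procedure that the protocol lacks and the cap rules out. The power loss needs a meaning of 30% that Section 11.2 does not give, and it comes with a lower false positive rate. Central review does not decide who is in the denominator, but it does limit local discretion over who counts as a responder, which is what drives a count rule.

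**Conclusion.** No change follows. Read as written, the plan enrols 14 and then 9, applies a count rule, requires a response of at least 4 weeks, has no replacement in cohorts 1 and 2, and estimates over the whole cohort. The three phrases then describe the same 23 patients, and the design delivers error 0.070, power 0.853 and early stopping 0.585, in line with what is stated. It is not true that one non-evaluable patient prevents the rule from being met.

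This rests on two assumptions: that 10% and 30% are rates among all treated patients, and that nobody in cohorts 1 and 2 is replaced. The text supports the second through its cap and says nothing against the first. Defining the word would only restate the denominator that Section 11.2 already uses for estimation. It would alter neither the decision nor the reported rate.

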## 1.0 OBJECTIVES

### Primary Objective

Estimate the efficacy of combination treatment with encorafenib and binimetinib, as measured by response rate (RANO criteria), in patients with recurrent BRAF V600E/K-mutated malignant glioma (MG) and anaplastic pleomorphic xanthoastrocytoma (PXAs).

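### For cohorts 1 and 2 the planned exact interval makes no stated allowance for the 14-patient futility stop, so its upper limits are too low at 2 to 4 responses of 23; the effect is minor

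*Combined protocol and SAP*

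**What the plan says.** Section 11.2 gives each of cohorts 1 and 2 a two-stage minimax design with one futility look. The stopping rule begins "If no more than 1 response (7%) was observed among the initial 14 patients in a cohort", in which case the cohort closes as negative. "Otherwise, nine more patients will be enrolled", and the regimen is taken forward "If at least 5 responses (at least 22%) were observed among the 23 evaluable patients".

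Later in the same section the response rate is defined, cohort by cohort, as responders "over number of patients in a cohort, as a binomial distribution (exact method) with 80% and 90% confidence intervals". Neither Section 11.2 nor Section 11.3 gives an ordering of outcomes, an adjusted estimate, or an interval that reflects the first-stage stop.

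Cohort 3 has 6 to 10 patients and no interim look; "This sample size is not based on statistical rationale but due to clinical feasibility".

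Section 1.0 words the primary objective as estimation: "Estimate the efficacy of combination treatment with encorafenib and binimetinib, as measured by response rate (RANO criteria").

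**The concern.** A one-stage exact interval assumes that the number of patients was fixed in advance. Here it depends on the first 14 results. A final count of 0 or 1 of 23 cannot occur, and 2 of 23 can arise only as two responses in the first 14 followed by none in the next nine.

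An upper limit asks which true rates would make a result this poor or poorer too unlikely. Under this design the poorer results include every cohort stopped at 14. The one-stage formula treats those cohorts as if they had gone on to 23 and could still have gathered responses. It therefore understates the chance of a poor result and sets the upper limit too low for cohorts that pass the look with few responses.

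Because estimation is the primary objective, the interval is a main result even for a negative cohort. An upper limit that is too low makes such a cohort look more firmly negative than its data allow. The counts concerned are not rare: the chance of ending at 2 to 4 of 23 is 35%, 40%, 32% and 10% at true rates of 10%, 15%, 20% and 30%.

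**Working it through.** **Inputs (all from Section 11.2).** First stage 14 patients, stop at 1 or fewer responses; second stage 9 more, total 23; success at 5 or more; null rate 10%, target rate 30%; 80% and 90% intervals, so 10% and 5% in each tail.

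**1. The plan's own figures.** Probability of stopping early at true rate p: S(p) = (1−p)^14 + 14p(1−p)^13. At 10%: 0.2288 + 0.3559 = 0.5846 (stated: at least 0.58). Probability of success: the sum over x ≥ 2 of P(x of 14) × P(at least 5−x of 9). This is 0.0699 at 10% (stated limit 0.10) and 0.8527 at 30% (stated: at least 0.85). The design figures are correct.

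**2. One-stage upper limit.** For s of n, the rate U that solves P(X ≤ s | n, U) = tail, with n = 14 for a stopped cohort and n = 23 otherwise.

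**3. Two-stage upper limit.** Order the outcomes 0/14, 1/14, 2/23, 3/23, …, 23/23. The observed proportions rise in the same order (0%, 7.1%, 8.7%, 13.0%, …), so ordering by stage and ordering by proportion agree here. For s of 23, U solves S(U) + f(2;U) + … + f(s;U) = tail. Here f(k;p) is the chance of reaching k of 23 after passing the look, and f(2;p) = 91p²(1−p)^21.

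Example, 2/23, 90% interval:
- At the one-stage limit, p = 0.2492, the fixed-n tail is 0.050. The two-stage tail is S + f(2) = 0.102 + 0.014 = 0.116, more than twice the intended 0.05.
- At p = 0.3024 the two-stage tail is 0.0065 + 0.0392 + 0.0043 = 0.0500. The two-stage limit is therefore 30.2%.

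**4. Limits, one-stage against two-stage.**

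| Result | 80% one-stage | 80% two-stage | 90% one-stage | 90% two-stage |
|---|---|---|---|---|
| 1/14 | 0.8–25.1% | 0.8–25.1% | 0.4–29.7% | 0.4–29.7% |
| 2/23 | 2.3–21.5% | 3.9–25.9% | 1.6–24.9% | 2.6–30.2% |
| 3/23 | 4.9–26.8% | 5.7–28.5% | 3.6–30.4% | 4.2–32.5% |
| 4/23 | 7.8–31.8% | 8.2–32.4% | 6.2–35.5% | 6.4–36.2% |
| 5/23 | 11.0–36.6% | 11.1–36.8% | 9.0–40.4% | 9.1–40.6% |

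**5. How often the upper limit lies below the true rate.** Just above a true rate of 30.36% (the one-stage 90% limit for 3/23), four results miss: 0/14, 1/14, 2/23 and 3/23. Their total probability is 0.0063 + 0.0385 + 0.0042 + 0.0238 = 0.0728, against 0.05. Just above 26.78% (the one-stage 80% limit for 3/23), the same four give 0.0127 + 0.0652 + 0.0094 + 0.0446 ≈ 0.132, against 0.10. These are the peaks. The excess is confined to narrow bands, mainly true rates of 25.1–25.9%, 26.8–28.5% and 31.8–32.4% (80% interval) and 29.7–30.2%, 30.4–32.5% and 35.5–36.2% (90% interval). The two-stage interval never exceeds 10.0% or 5.0%.

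**6. Two-sided coverage.**

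| True rate | 80% one-stage | 80% two-stage | 90% one-stage | 90% two-stage |
|---|---|---|---|---|
| 10% | 93.0% | 93.0% | 97.8% | 97.8% |
| 15% | 95.4% | 95.4% | 95.4% | 95.4% |
| 20% | 88.5% | 88.5% | 92.9% | 92.9% |
| 30% | 86.8% | 86.8% | 92.7% | 93.1% |
| Minimum over all rates | 78.9% | 80.2% | 90.4% | 90.7% |

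The one-stage 80% interval is below nominal only for true rates of 25.07% to 25.18%.

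**The case against.** The strongest reply is that the planned intervals do almost everything they promise. Section 11.2 offers two-sided 80% and 90% intervals, not one-sided bounds. The 90% interval never falls below nominal coverage, the 80% interval does so only in a sliver of true rates, and coverage at 10%, 15% and 20% is identical under both methods. All of that stands and limits the point to a minor one. What remains is that an interval called exact should hold its error in each tail, and this one does not hold it in the upper tail.

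Two stronger readings are tempting.

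- A reader might infer that the reversal across the stopping boundary proves the defect: the 90% upper limit is 29.7% for a cohort stopped at 1/14 but 24.9% for one that passed the look and ended at 2/23. Part of that gap is simply 23 patients against 14. Two unrelated fixed-size samples with these counts would give the same limits, so the reversal is only an illustration. The evidence is the miss rate in step 5.
- A reader might infer that the planned interval wrongly rules out the target, which the plan calls "an alternative of 30% tumor response rate to be clinically desired treatment effect". At 2/23 the 90% one-stage interval does exclude 30% and the two-stage interval does not, but only just (30.24%). At the 80% level both exclude it. At 1/14 both 90% intervals exclude it. If the true rate were 30%, 2/23 would occur with probability 0.5%.

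It can also be said that the text does not name Clopper-Pearson and that a two-stage interval is an exact binomial method too. That is fair: the one-stage reading rests on the absence of any stage adjustment. It is still the plain reading of the sentence, and naming the method settles it.

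Finally, a two-stage interval depends on the stage sizes, and a cohort may not finish at exactly 14 or 23. This objection stands, and the fix has to cover it.

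**Conclusion.** The point holds and is minor. For cohorts 1 and 2 the interval as written does not match the two-stage sampling. Its 90% upper limits are 5.3, 2.1 and 0.7 points too low at 2, 3 and 4 of 23 (30.24 − 24.92, 32.47 − 30.36, 36.19 − 35.49). At 5 of 23 the limits move by 0.2 points or less.

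The documents do not support a reading that the design itself is at fault. The go/no-go rule uses response counts, so its false-positive rate, power and stopping probability are as stated, and no decision changes at any count. Nor do they support a claim of general under-coverage. Cohort 3 is unaffected.

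The result assumes that the unadjusted interval is Clopper-Pearson, that the look and the final analysis take place at exactly 14 and 23, and that the patients in the denominator of the estimate are the same ones counted under the stopping and success rules.

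**What to change.** In Section 11.2, state that for cohorts 1 and 2 the 80% and 90% intervals are two-stage exact intervals with stagewise ordering, computed with the stage sizes actually realised. That covers a cohort that closes between 14 and 23, or that enrols past 14 before the look is resolved. Keep the simple proportion as the point estimate, and keep the one-stage exact interval for cohort 3.

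The cost is a few sentences and a short piece of code. No patients are added and the decision rule is untouched: the 80% lower limit first exceeds 10% at 5 of 23 under either method (11.0% one-stage, 11.1% two-stage; at 4 of 23, 7.8% and 8.2%). The downside is slightly wider intervals at low counts. At a true rate of 10% the expected width rises from 21.5 to 21.9 points (80% interval) and from 26.2 to 26.9 points (90% interval). At a true rate of 30% it rises by about 0.1 points.
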